---

## 1. STUDY RATIONALE

Intracranial atherosclerotic arterial stenosis (ICAS) is an important cause of stroke in the US, and is especially prevalent in blacks, Asians, and Hispanics. Over the past 20 years, [name], one of the Co-PIs of this pilot study has led consecutive NIH funded multicenter clinical trials to test therapies for preventing stroke in subjects with ICAS: The WASID trial showed that aspirin was as effective as warfarin for preventing stroke, and the SAMMPRIS trial showed that aggressive medical management (AMM) consisting of dual antiplatelet therapy and intensive risk factor management was more effective than percutaneous transluminal stenting for preventing stroke in recently symptomatic subjects with ICAS. However, among high-risk subjects (those with severe [70-99%] stenosis who presented with a stroke [rather than a TIA]), the 1-yr rate of recurrent stroke was 20.7% despite aggressive medical management. Therefore, more effective therapies to prevent stroke in these high-risk patients remains an urgent need.

One promising novel treatment is remote limb ischemic conditioning (RLIC), which involves producing repetitive, transient, non-injurious ischemia of a limb by inflating a blood pressure cuff proximally with the intention of protecting a distal organ (in this case, the brain) from subsequent ischemia. One of the co-investigators in our group ([name] at the Medical College of Georgia (MCG)) has conducted pre-clinical studies using a bilateral carotid artery stenosis mouse model that showed RLIC increases cerebral blood flow (CBF), most likely by releasing nitrite into the circulation, and acts as a powerful neuroprotectant and vasculoprotectant. Additionally, two pilot randomized clinical trials performed in China showed that symptomatic subjects with ICAS treated with bilateral upper extremity RLIC daily for 180 or 300 days and medical management had a 70-75% lower rate of stroke compared with subjects treated with medical management alone. Although these preclinical studies and the two small Chinese pilot studies might suggest that the next step is to perform a multicenter randomized Phase II trial to determine the potential efficacy of RLIC in high-risk subjects with ICAS in the US, the lack of reliable data on how RLIC works in humans mandates an initial earlier phase trial to study potential mechanisms of action of RLIC in subjects with ICAS.

## 2. PRIMARY AIMS AND LONG-TERM GOAL

As a first step to collect preliminary data on the potential mechanisms of action of RLIC in humans, we will perform a small multicenter randomized pilot clinical trial of 10 subjects with ICAS at 4 participating sites (MUSC, MCG, UCLA and the University of Southern California (USC)) to accomplish the following **primary aims**:

[figure not shown]
- (1) Estimate the variability in CBF (measured by arterial spin labeling and perfusion MRI) and levels of putative biomarkers of the conditioning response (vasodilatory, inflammatory, fibrinolytic, microRNA) in the two treatment groups at enrollment and after 30 days of treatment.
- (2) Compare the changes in CBF and putative blood biomarkers of the conditioning response from enrollment to 30 days between the two treatment groups.
- (3) Obtain preliminary feasibility, tolerability and adherence data on the use of a RLIC device for secondary stroke prevention in subjects with ICAS.

This study will provide preliminary data to enable planning of a subsequent grant submission to NIH to perform a Phase I / II trial with the following goals: to provide more rigorous data on the mechanisms of action of RLIC, and to determine the potential efficacy of RLIC for preventing stroke in high-risk subjects with ICAS. Our ultimate goal is to perform a large randomized multicenter NIH-funded Phase III trial to determine the efficacy of RLIC for preventing stroke.

### 3. OVERVIEW OF STUDY DESIGN

The design of the study is illustrated in Figure 1 below. In this prospective randomized pilot study, 10 eligible high-risk subjects with ICAS will be randomized to RLIC (bilateral upper extremity (BUE) daily for 30 days) plus AMM (n=5) or AMM alone (n=5). The AMM, which will be started at study enrollment and continued until close-out in all subjects, will consist of aspirin 325 mg per day, clopidogrel 75 mg per day, and risk factor management primarily targeting a systolic BP < 140 mmHg and LDL cholesterol < 70 mg /dl. All subjects will undergo baseline brain arterial spin labeling (ASL) and perfusion MRI to measure CBF and have blood drawn for biomarkers 3-5 days after randomization to allow for washout of any effect from the test RLIC treatment that will be done prior to randomization to determine the subjects' tolerability to RLIC treatment (see section 5 for more details on screening test). The period of 3-5 days will provide flexibility for scheduling these tests. After the baseline MRI and biomarker tests are completed, the subjects randomized to RLIC will begin daily RLIC for 30 days. Each daily BUE RLIC treatment will consist of 4 cycles of 5-minute inflations of both blood pressure cuffs simultaneously to a pressure of 200 mm Hg with 5 minutes of reperfusion between each inflation using the Doctormate device (see Figure 2). All subjects will return for their close-out visits 33-35 days after enrolling in the study and will undergo brain ASL and perfusion MRI and have blood drawn for biomarkers at that visit. The study will be conducted at 4 sites (MUSC, MCG, UCLA, USC) to enable us to evaluate the consistency of CBF measurements across multiple sites and to ensure that the recruitment target of 10 subjects will be met in time to allow for the subsequent NIH grant submission in 2017.

Figure 1. Overview of Study Design

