## **9. MRI MEASUREMENTS OF CBF AND OTHER PERfusion PARAMETERS**

ASL MRI will be used to provide quantitative measurements of CBF in all 10 subjects in the study (at baseline and at close-out). ASL does not require the injection of contrast material and can be repeated over time without risk to patients. **We will use a standardized ASL protocol agreed upon by the study radiologists and physicists at the 4 participating sites that can be applied to different MRI scanner platforms.** Each subject will undergo all MR studies for this pilot on the same scanner to limit slight variations in images from scanner to scanner. We have already tested the feasibility of using our planned ASL MRI protocol under a MCG / UCLA IRB-approved protocol. Six subjects with recent stroke from ICAS underwent ASL MRI before and after one RLIC treatment, a mean of 4.6 hours apart. The de-identified scans were sent to UCLA where [name] performed CBF analyses and readings blinded to pre- and post-RLIC treatment. After just 1 cycle of RLIC, these subjects showed mean increases of CBF of 8%-28% in the MCA and PCA territories on the infarct side vs. the normal side. While quantitative CBF obtained with ASL MRI is the primary MR outcome in this pilot, we will also utilize dynamic susceptibility contrast enhanced perfusion MR imaging (DSC-PWI) to assess the effectiveness of secondary brain perfusion parameters (such as cerebral blood volume and cerebrovascular transit times).

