## **11. RANDOMIZATION, BLINDING, AND DATA MANAGEMENT**

Subjects will be randomized 1:1 using a pre-generated exact central randomization list that controls for moderate imbalances at the site level. All study data will be entered directly by either the study PI or stroke coordinator at each site in the RedCap data management system developed at MUSC for the study. Initial data checking will be performed by the system before the data can be saved to prevent low level data errors. When the data are transferred to the study biostatistician for analysis and report generation, further data quality checks will be conducted by SAS. Study data will be retained on a secure server at the Department of Public Health Sciences at MUSC.

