## **12. STATISTICAL ANALYSES**

To estimate the variability in CBF and biomarkers, all of which are continuous measures, simple summary statistics will be reported for the baseline and close-out measurements in each group. With five imaging samples per group, the precision of the 90% confidence interval around the mean would be  $\pm 0.95$  for a SD of 1, and, as an example, would increase to  $\pm 7.63$  for a SD of 8. We will also evaluate the changes in CBF and biomarkers from baseline to close-out in the two groups using means and 90% confidence intervals. Here, the precision of the resulting confidence interval is  $\pm 9.4$  when the SD is 8; that is, if RLIC yields a mean 10% change in CBF and sham RLIC yields a mean 0% change in CBF the resulting 90% confidence interval is (0.6, 19.4) for the difference in percent change in CBF. Finally, with a sample size of N=5, we will be able to estimate the correlation between CBF and biomarkers for each arm with an 90% confidence interval of 0.5 (-0.5, 0.9) in the case of an observed moderate correlation. Interpretation of the summary statistics will be complimented with graphical approaches including boxplots to assess distributions within treatment arms, and funnel plots to assess differences at the site level.

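### Ten subjects at four sites, each scanned on one scanner, cannot show whether CBF measurements are consistent across sites, and the planned funnel plots cannot settle it either way

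*Combined protocol and SAP*

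**What the plan says.** Section 2 describes a "randomized pilot clinical trial of 10 subjects with ICAS at 4 participating sites". Section 3 gives two reasons for the four sites. The first is "to enable us to evaluate the consistency of CBF measurements across multiple sites"; the second is reaching the recruitment target in time for the next grant submission.

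Section 9 plans a standardized ASL protocol "that can be applied to different MRI scanner platforms", with a scan at baseline and another at close-out. It adds: "Each subject will undergo all MR studies for this pilot on the same scanner". Section 11 allocates subjects 1:1 from a central list that limits imbalance at site level. No number of subjects per site is set.

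The only site-level analysis is in Section 12: "funnel plots to assess differences at the site level". Section 12 does not say what is plotted (baseline, close-out or change; CBF or biomarkers), at what level the limits are drawn, or what would count as consistent. The text available for review describes no phantom, no volunteer scanned at more than one site, and no agreement statistic. Cross-site consistency is not among the three primary aims in Section 2.

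**The concern.** Comparing sites on absolute CBF needs something common to the sites: the same person or object measured on several scanners, or enough patients per site for patient differences to average out. The plan has neither. Subjects are nested within scanner and site. They may differ in the affected artery, in stenosis within 70-99%, and in time since stroke up to 30 days, and all of these are mixed with any scanner difference. A better display cannot undo that.

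What is at stake is the reading of the result. The pilot is meant to support planning of a multicentre trial. A reader who has been told that four sites were used to evaluate consistency will tend to read a quiet funnel plot as evidence for it and an outlying site as evidence against it. Neither reading is justified.

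**Working it through.** **The plan's own precision figures.** Section 12 gives 90% half-widths, and these reproduce with t quantiles:
- Group mean, n = 5: t(0.95; 4 df) × SD/√5 = 0.953 for SD 1 and 7.627 for SD 8 (stated 0.95 and 7.63).
- Difference between arms: t(0.95; 8 df) × 8 × √(2/5) = 9.41 (stated 9.4).

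None of the stated figures concerns a comparison of sites.

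**Inputs for the site question.**
- N = 10 subjects and 4 sites (Sections 2 and 3), so 10/4 = 2.5 per site.
- Site sizes 3/3/2/2: assumed, as the most even split possible.
- SD 8: the example value in Section 12. The flagging rates below do not depend on it, because bias is expressed in SD units.
- 90% limits, centred on the overall mean, SD treated as known: assumed, to match the 90% level used in the rest of Section 12.
- Share of CBF variance due to site: not given in the documents, so a range is shown.

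**Funnel limits.** 1.645 × 8/√n = ±7.6 for n = 3 and ±9.3 for n = 2.

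**No site effect.** In simulation, at least one of the four sites falls outside in about 19% of trials.

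**One site biased by one SD (8 units).** The biased site also shifts the overall mean, so its expected deviation is 8 × (1 − n/10), and the SD of the deviation is 8 × √(1/n − 1/10).
- n = 3: deviation 5.6, SD 3.86. P(flag) ≈ P(Z > (7.60 − 5.6)/3.86) = P(Z > 0.52) ≈ 30%.
- n = 2: deviation 6.4, SD 5.06. P(flag) ≈ P(Z > (9.31 − 6.4)/5.06) = P(Z > 0.57) ≈ 28%.

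That is about 29% overall.

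**Larger site effects (simulation).**

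| Setting | At least one site flagged |
|---|---|
| No site effect | 19% |
| Site share of variance 0.25 | 45% |
| Site variance equal to subject variance (share 0.50) | 70% |
| Two-SD bias at one site | 80% (site of 2) to 86% (site of 3) |

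**A formal test would do no better.** A one-way random-effects analysis has 3 and 6 df. The power of a 10%-level F test for site is 21%, 31% and 47% when the ratio of site to subject variance is 0.25, 0.5 and 1. The plan does not propose this test; it is shown only to gauge the information available.

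**What a null result allows.** The effective site size is n0 = (10 − 26/10)/3 = 2.47, where 26 = 3² + 3² + 2² + 2². If the observed F is 1, the upper bound of the 90% interval uses F/F(0.05; 3, 6) = 1/0.1118 = 8.94. The site share is then (8.94 − 1)/(8.94 − 1 + 2.47) = 0.76.

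**Uneven accrual.** Splits of 4/3/2/1, 4/4/1/1 and 7/1/1/1 lower the F-test power at a site share of 0.25 from 25% to 24%, 23% and 20%.

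**The case against.** The strongest reply is that this is a ten-subject descriptive pilot. Consistency is not a primary aim, recruitment justifies four sites by itself, and evaluating consistency need not mean estimating a variance component. All of that stands, and it limits the weight of the point. It does not give the design the property that Section 3 claims for it.

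The one-scanner rule is also sound for its own purpose. A constant additive scanner offset cancels from an absolute change from baseline, so the comparison of changes between arms is protected. The fault lies in the consistency purpose, not in that rule. Nor does Section 12 say that the funnel plots show CBF site means; they may also serve the 13 biomarkers, and nothing here argues against that use.

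Three stronger readings are tempting but not supported:
- A reader might infer that all four points would stay inside the limits even with a large scanner bias. The figures show otherwise: a two-SD bias at one site puts some point outside in 80-86% of trials.
- A reader might infer that a one-SD bias always stays hidden. It is flagged about 29% of the time.
- A reader might infer that Aim 1's total SD is wrong because it contains scanner variance. For planning a multicentre trial, an SD that includes between-site variation can be the relevant one for absolute CBF.

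The documents also do not say that the funnel plots will be used to claim consistency in the grant. That is a risk of interpretation, not a stated plan.

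**Conclusion.** The concern holds in a limited form: the design does not have a property that Section 3 states as a reason for it. Scanner and patient differences in absolute CBF are fully confounded, whatever the split across sites. Site and within-site variance can formally be estimated, but on 3 and 6 df the result is too imprecise to use. The funnel plot gives a false flag in about one trial in five and misses a one-SD bias at a given site in about seven of ten. Even when it correctly flags a large effect, it cannot say whether the scanner or the patient mix is the cause.

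The rates rest on the assumed 3/3/2/2 split, 90% limits and a known SD; the confounding rests on none of these. The change is worth making because it governs what may be concluded about sites. It does not touch the primary aims, the sample size or the conduct of the trial.

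**What to change.** **Section 3.** Replace the consistency purpose with feasibility of running the common ASL protocol at four sites, reported as the number of technically usable scans out of the 20 planned (10 subjects × 2), by site. Keep the recruitment reason.

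**Section 12.** Replace the CBF funnel plots with a listing or plot of each subject's baseline, close-out and change in CBF, identified by site and scanner. Show the pooled within-site SD (6 df) beside the total SD, as description only, since it has the same imprecision and the same mixing of scanner and patient. State that scanner and patient differences are confounded and that no conclusion on cross-site consistency will be drawn.

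**Cost.** Wording and one table or figure, with no extra scans or subjects. The downside is giving up a stated secondary purpose of the four-site design. If the sponsor wants to keep that purpose, the design needs a crossed element, such as travelling volunteers or a perfusion phantom, with a named agreement measure. That would be a real addition to the study.

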### 4. SUBJECT SELECTION CRITERIA

**The Target Population** are subjects between 30 – 90 years of age with stroke within the previous 30 days that is attributed to 70-99% atherosclerotic stenosis of a major intracranial artery (carotid, middle cerebral, vertebral or basilar). The full inclusion and exclusion criteria are similar to the SAMMPRIS trial  (referred to in section 1 above) with the following exceptions: 1) Subjects with TIA will be excluded because of their excellent outcome on AMM in SAMMPRIS. 2) The upper age limit in this pilot is 90 rather than 80, given the positive response to RLIC in octogenarians in the 2nd Chinese trial. 3) CT angiography (CTA) or magnetic resonance angiography (MRA) measurements of 70-99% intracranial stenosis will be sufficient for enrollment in this study, whereas catheter angiography was required in SAMMPRIS. (Catheter angiography is expensive and has some risk that is difficult to justify in a medical management trial). 4) Diabetic subjects taking sulfonylureas will be excluded because these drugs block ATP-sensitive potassium channels that are thought to play a key role in the protective effect of RLIC. The full inclusion and exclusion criteria for this pilot study are provided below.

### **Inclusion Criteria:**

1. Symptomatic cerebral infarction within 30 days of enrollment attributed to 70-99% stenosis of a major intracranial artery (carotid artery, MCA stem (M1), vertebral artery, or basilar artery) that is documented by any of the following: MRA, CTA, or catheter angiography. Percent stenosis will be measured according to WASID criteria ( $= 1 - [Ds / Dn] \times 100\%$  with Ds [diameter of stenosis] and Dn [diameter of normal vessel]).
2. Modified Rankin score of  $\leq 3$
3. Age  $\geq 30$  years and  $\leq 90$  years.
  - Subjects 30-49 years are required to meet at least one additional criteria (i-vi) provided in the table below to qualify for the study. This additional requirement is to increase the likelihood that the symptomatic intracranial stenosis in subjects 30-49 years is atherosclerotic.

i. insulin dependent diabetes for at least 15 years
ii. at least 2 of the following atherosclerotic risk factors: hypertension (BP $\geq 140/90$ or on antihypertensive therapy); dyslipidemia (LDL $\geq 130$ mg /dl or HDL $< 40$ mg/dl or fasting triglycerides $\geq 150$ mg/dl or on lipid lowering therapy); smoking; non-insulin dependent diabetes or insulin dependent diabetes of less than 15 years duration; family history of any of the following: myocardial infarction, coronary artery bypass, coronary angioplasty or stenting, stroke, carotid endarterectomy or stenting, peripheral vascular surgery in parent or sibling who was $< 55$ years of age for men or $< 65$ for women at the time of the event
ii. history of any of the following: myocardial infarction, coronary artery bypass, coronary angioplasty or stenting, carotid endarterectomy or stenting, or peripheral vascular surgery for atherosclerotic disease
iv. any stenosis of an extracranial carotid or vertebral artery, another intracranial artery, subclavian artery, coronary artery, iliac or femoral artery, other lower or upper extremity artery, mesenteric artery, or renal artery that was documented by non-invasive vascular imaging or catheter angiography and is considered atherosclerotic
v. aortic arch atheroma documented by non-invasive vascular imaging or catheter angiography
vi. any aortic aneurysm documented by non-invasive vascular imaging or catheter angiography that is considered atherosclerotic

4. Negative pregnancy test in a female who has had any menses in the last 18 months
5. Subject is willing and able to return in 30 days for close-out visit for the study
6. Subject is available by phone
7. Subject is able to apply the conditioning device or has access to another person (family member, friend) who can assist with application of conditioning device if needed
8. Subject understands the purpose and requirements of the study, can make him/herself understood, and has provided informed consent
9. Subject is able to undergo brain MRI

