14. Major surgery (including open femoral, aortic, or carotid surgery, cardiac) within previous 30 days or planned in the next 30 days after enrollment
15. Indication for warfarin or heparin beyond enrollment (**NOTE: exceptions allowed for subcutaneous heparin for deep vein thrombosis (DVT) prophylaxis while hospitalized**)
16. Diabetic subjects taking sulfonylurea drugs
17. Severe neurological deficit that renders the subject incapable of living independently
18. Dementia or psychiatric problem that prevents the subject from following the protocol reliably
19. Co-morbid conditions that may limit survival to less than 3 months
20. Pregnancy or of childbearing potential and unwilling to use contraception for the duration of this study
21. Claustrophobia requiring sedation for MRI or any metallic implants or MRI incompatible devices that do not permit the patient to have an MRI
22. Enrollment in another study that would conflict with the current study

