## 8. BLOOD BIOMARKER MEASUREMENTS

The blood biomarkers that will be measured are putative biomarkers of RLIC and known inflammatory and fibrinolytic markers associated with the development or progression of ICAS, or increased risk of stroke in patients with ICAS. These consist of: Nitrite, IL-10, SDF1, Micro RNA 144, Lp-PLA2, IL-6, hsCRP, Soluble E-selectin, ICAM, MMP-9, PAI-1, tPA, and ADMA. We will measure the blood biomarkers at baseline and close-out (33-35 days after enrollment) in all 10 subjects. All blood biomarkers will be mailed to the Blood Biomarker Core at MCG where the levels of biomarkers will be measured blinded to site, subject, treatment assignment and time point.

**Figure 2.** The RLIC device used in the Chinese trials will be used in this pilot study and is shown being applied to [name], a Co-PI of this pilot study at Georgia Regents University (center)

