d.) All of the medications used in this study (aspirin and clopidogrel and the medications to control risk factors) have been approved by the Food and Drug Administration (FDA) for the conditions for which they will be prescribed in this study and are not investigational. The major side effects of aspirin are major hemorrhage and peptic ulceration. Other possible side effects of aspirin include heartburn, ringing in the ears, nausea and vomiting. The most common side effects of clopidogrel are skin rash, bruising, itching, nausea, vomiting, diarrhea, intestinal discomfort. A less common but more serious side effect of clopidogrel is major gastrointestinal or brain hemorrhage. The most serious side effect of clopidogrel is a clotting disorder called thrombotic thrombocytopenic purpura (TTP) but this is very rare (1 in 15,000-20,000 treated subjects). The combination of clopidogrel and aspirin is commonly used for 90 days after stroke or TIA in patients with intracranial stenosis following the SAMMPRIS trial and will be prescribed for the duration that subjects participate in this pilot study (33-35 days). The combination of aspirin and clopidogrel is associated with a significantly higher risk of major bleeding compared with clopidogrel or aspirin alone. The risks associated with statin therapy are a persistent increase in liver enzymes (0.0 - 0.4%), myalgia (2.8%), muscle weakness with increase in CK levels > 10 x upper limit of normal (0.03 - 0.1%), and rarely rhabdomyolysis that can potentially lead to renal failure. The risks associated with antihypertensive medications include hypotension, dizziness, headaches, weakness,

allergic reactions, diarrhea, hypokalemia or hyperkalemia depending on the type of blood pressure medication taken, cough (with ACE inhibitors), and angioedema (ACE inhibitors).

e.) There is the risk of loss of confidentiality

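### Exclusion 14 looks 30 days past enrollment, but close-out falls on days 33-35, so major surgery planned for days 31-35 is not excluded; the 30 days in Inclusion 5 need the same alignment

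*Combined protocol and SAP*

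**What the plan says.** Two eligibility criteria in Section 4 use a forward window of 30 days.

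- Exclusion 14 covers major surgery, including open femoral, aortic, carotid and cardiac surgery, that was done or is planned "within previous 30 days or planned in the next 30 days after enrollment". Its count starts at enrollment.
- Inclusion 5 requires: "Subject is willing and able to return in 30 days for close-out visit for the study". It does not say from when the 30 days run.

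The schedule is longer.

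- Section 3: "All subjects will return for their close-out visits 33-35 days after enrolling in the study". At close-out they "will undergo brain ASL and perfusion MRI and have blood drawn for biomarkers at that visit".
- Section 8, for the blood markers: "We will measure the blood biomarkers at baseline and close-out (33-35 days after enrollment) in all 10 subjects".
- Section 3 has subjects undergo baseline MRI and "have blood drawn for biomarkers 3-5 days after randomization to allow for washout of any effect from the test RLIC treatment". After that baseline, "the subjects randomized to RLIC will begin daily RLIC for 30 days".
- Section 13, in its discussion of medication risks, gives the length of participation as 33-35 days. It does not itself time the MRI or the blood draw.

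**The concern.** Aims 1 and 2 in Section 2 rest on paired values of cerebral blood flow and blood markers, at baseline and close-out, in five subjects per arm. Section 12 states its precision for five per group and makes no allowance for a missing close-out. A criterion that keeps out subjects with major surgery planned during follow-up should reach the end of follow-up. Exclusion 14 stops 3-5 days before it.

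A subject with major surgery booked for day 31 or 32 passes that criterion as written. Such surgery could come between the end of the window and the close-out measurement, or fall on the same day. In the conditioning arm it could also overlap the last treatment sessions. The pair might then be lost, or its second value might be taken in circumstances that the criterion appears designed to avoid.

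Inclusion 5 raises a lesser question. It is applied at screening, before randomization and baseline, and a coordinator may count its 30 days from that point and so arrive at a different date from Section 3.

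**Working it through.** **Timing.** Take enrollment and randomization as day 0. The plan counts baseline from randomization and close-out from enrollment, so treating the two as the same day is an assumption.

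| Item | Source | Days |
|---|---|---|
| End of planned-surgery window | Section 4, Exclusion 14 | 30 |
| Baseline MRI and blood | Section 3 | 3-5 |
| 30th session, started on the baseline day | baseline + 29 | 32-34 |
| 30th session, started the next day | baseline + 30 | 33-35 |
| Close-out MRI and blood | Section 3 (both), Section 8 (blood) | 33-35 |

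The shortfall to close-out is 33 - 30 = 3 to 35 - 30 = 5 days. The days not covered are 31 up to the close-out day, at most 31-35. The two session rows apply to the conditioning arm only; the close-out row applies to both arms.

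**Does another criterion cover those days?**

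- Exclusions 1 and 2 have no time limit, but they concern stenting, angioplasty or other device treatment of the target lesion, and angioplasty or stenting of a tandem extracranial vessel. Major surgery in general is outside both.
- Inclusion 5 (return for close-out) and Inclusion 9 (able to undergo brain MRI) catch surgery that prevents attendance or scanning. They do not catch surgery after which the subject can still attend.

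So no other criterion closes the gap.

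**Scale of one lost pair.** Section 12 prints results but no formula. A two-sample t interval reproduces them:

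half-width = t(0.95, n1 + n2 - 2) × SD × √(1/n1 + 1/n2)

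- 5 v 5, SD 8: 1.860 × 8 × √(1/5 + 1/5) = 9.41. With a difference of 10 this gives (0.6, 19.4), as stated.
- 5 v 4, SD 8: 1.895 × 8 × √(1/5 + 1/4) = 10.17, giving (-0.2, 20.2).
- Mean of one arm, n = 5: 2.132/√5 = 0.95 SD, as stated.
- Mean of one arm, n = 4: 2.353/√4 = 1.18 SD.

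These figures describe one close-out lost for any reason. They do not estimate the effect of the wording, since the documents give no rate at which surgery would be planned for days 31-35. Aligning the wording leaves the planned 5 v 5 interval at (0.6, 19.4).

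**The case against.** The strongest reply concerns Inclusion 5. A reader might infer that someone away on days 31-35 satisfies it. The documents do not support that. The criterion requires return for the close-out visit itself, and Section 3 fixes that visit at days 33-35, so a subject who cannot attend then arguably fails it already. Thirty days from a baseline on day 3 or day 5 is day 33 or day 35, and Aim 2 in Section 2 also uses 30 days as the label for the close-out time point. Inclusion 8 further requires that the subject understands what the study asks. This reply stands: Inclusion 5 is unclear, but it cannot be shown to admit the wrong people.

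A reader might also infer that eligibility as a whole looks only 30 days ahead. It does not. Exclusion 19 looks 3 months ahead, Exclusion 20 covers the whole study, and Exclusions 1 and 2 have no time limit.

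It is tempting to add that surgery would shift the measured blood markers. The documents say nothing on this, and the point does not need it.

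Nor should weight be put on the 5 v 4 interval crossing zero. Section 12 plans estimation with 90% intervals and no hypothesis test, and a stroke, a withdrawal or a failed scan would widen the interval by the same amount.

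Finally, some text between Sections 5 and 6 was not available for this review, so a definition of enrollment there cannot be ruled out. It would not remove the mismatch, because Exclusion 14 and the Section 3 close-out are both counted from enrollment.

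None of this answers the gap in Exclusion 14. That criterion names its own starting point, and no alternative reading extends it to day 33.

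**Conclusion.** The point holds in a narrow form and is minor. Exclusion 14 ends 3-5 days before close-out, so major surgery planned for days 31-35 is allowed on the text even though it could precede or coincide with the only post-treatment measurement. Inclusion 5 has an unstated starting point and should be brought into line with the same schedule; it is an ambiguity and no more.

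The expected effect is small. The frequency of such surgery is not given and is assumed low, and no sample size or interval in the plan changes. The conclusion rests on reading Exclusion 14 literally. The day numbers for the conditioning sessions also assume that randomization and enrollment fall on the same day, but the 30 against 33-35 comparison does not need that assumption.

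**What to change.** Reconcile Section 4 with Sections 3 and 8 and with the participation length in Section 13:

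- Exclusion 14: let the planned-surgery look-ahead run from enrollment through completion of the close-out visit, in place of a fixed 30 days.
- Inclusion 5: refer to the close-out visit 33-35 days after enrollment.

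Appendix 1 labels its week 4 entry as the close-out visit without saying from when the weeks are counted; check it against the same schedule at the same time.

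The cost is two phrases in Section 4. The downside is that a rare subject with surgery planned for days 31-35 is screened out or rescheduled. No statistical text has to be rewritten.
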